4.1. Site Identification

A simple survey containing a series of queries will be completed by those sites identified on the master list for each country to determine their eligibility to participate in the study.

The queries within the survey will include the following:

- Site details (such as overall number of patients)
- Number of DVT/SVT patients treated at each site
- Types and number of physicians/specialists who are managing such patients
- Diagnostic criteria employed (such as physical assessment; imaging techniques, other blood tests)
- Diagnostic tools/capabilities within each site.

The survey will not contain any indications of overall objective of the study.

Eligible sites will be stratified by geographical region and between 18 and 36 sites that are representative of each country's population distribution will be

randomly selected and invited to complete a feasibility study as a pre-cursor to being finally selected for recruitment into the study.

4.2. Feasibility Study

A feasibility study will be conducted in those randomly selected eligible sites to determine the availability of select data components within the medical chart. The feasibility study will comprise a simple questionnaire which will contain the variables of interest as a check list. Physicians who could act as the lead investigator at each eligible site will be asked to review the medical charts of those SVT patients meeting the criteria for the study, to determine the variables/data of interest that are routinely available for each patient. The patient charts to be reviewed will be representative of those treated by each physician within each site. Additionally, the number of patient charts to be reviewed will be equivalent to the number of eligible patients a site may have available for the main study (within the upper limits set out in the main study protocol).

The variables of interest will include as follows:

- Age
- Gender
- Renal status
- Presence/absence of concomitant DVT
- Length of thrombus
- Distance from sapheno-femoral junction
- Diagnostic procedures performed (e.g. ultrasound or other objective tests)
- Prescribed fondaparinux dose and duration.

This questionnaire will not contain any indication with regards to the overall objective of the study.

Between 12 and 18 eligible sites, proportionate to the country's population and representative of the country's main geographical regions, successfully completing the feasibility study will be invited to progress to the main study.

4.3. Outcome

The primary outcome measure will be the proportion of patients for whom **both** an ultrasound (or other diagnostic imaging procedure), was performed in order to rule out concomitant DVT prior to patients commencing fondaparinux therapy **and** that the correct dose of fondaparinux (2.5mg or 1.5mg) was prescribed (i.e. adherence to fondaparinux prescribing information – see Appendix 9.1). This will be evaluated overall and in each country.

A sensitivity analysis of the primary outcome will be conducted incorporating the length of the thrombus (>5 cm) and/or its distance from the sapheno-femoral junction (>3 cm), pending the availability of the data.

Secondary outcomes will evaluate the proportion of patients prescribed the correct dose of fondaparinux, as well as those who had an ultrasound (or other diagnostic imaging procedure) performed to rule out concomitant DVT. In addition, when available, the proportion of patients having a thrombus >5 cm and a distance from the sapheno-femoral junction of at least 3 cm will be estimated.

Similar to the primary outcome, these will also be evaluated overall and in each country.

Please note that patient outcome data following fondaparinux prescription will not be collected.

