2. OBJECTIVE

The primary objective is to evaluate physicians' adherence to fondaparinux prescribing information for the treatment of patients with SVT of the lower limbs without concomitant DVT.

The primary endpoint of the study is the proportion of patients with isolated SVT of the lower limbs treated with fondaparinux, for whom the prescribing information was followed (i.e., an ultrasound, or other diagnostic imaging procedure, was performed in order to rule out concomitant DVT prior to patients commencing fondaparinux therapy and the correct dose of fondaparinux [either 2.5 or 1.5mg] was prescribed).

Based on the availability of data, as identified in the feasibility phase of this study, a sensitivity analysis of the primary endpoint will be conducted, incorporating the length of the thrombus (>5 cm) and/or its distance from the sapheno-femoral junction (>3 cm).

Secondary endpoints of the study include:

- The proportion of patients with SVT of the lower limbs treated with fondaparinux, for whom an ultrasound, or other diagnostic imaging procedure, was performed in order to rule out concomitant DVT prior to patients commencing fondaparinux therapy
- The proportion of patients with SVT of the lower limbs treated with fondaparinux, for whom either 2.5mg or 1.5mg fondaparinux was prescribed.

Pending the availability of the data as identified from the feasibility study, the following will also be included as secondary endpoints of the study:

 The proportion of patients with SVT of the lower limbs treated with fondaparinux, for whom the length of thrombus was measured (<5 cm being non-adherence) The proportion of patients with SVT of the lower limbs treated with fondaparinux, for whom the distance from the sapheno-femoral junction was recorded (<3 cm being non-adherence).

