5.2.1. Primary Analyses

Adherence estimates with confidence intervals will be derived using generalised estimating equations (GEE) overall and for each country [8]. The GEE will explicitly take into account the nesting of patients, per physician, within a medical practice.

Adherence in the current study will be defined as performing CUS, or other diagnostic imaging procedure, in order to rule out concomitant DVT prior to patients commencing fondaparinux therapy and ensuring that the recommended dose of fondaparinux is prescribed.

A sensitivity analysis will be conducted incorporating the length of the thrombus and the distance of the thrombus from the sapheno-femoral junction into the primary endpoint if the data is available.

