9. APPENDICES

9.1 Fondaparinux prescribing information

PRESCRIBING INFORMATION FOR USE IN PATIENTS WITH SVT

Treatment of superficial-vein thrombosis

The recommended dose of fondaparinux is 2.5 mg once daily, administered by subcutaneous injection. Patients eligible for fondaparinux 2.5 mg treatment should have acute, symptomatic, isolated, spontaneous superficial-vein thrombosis of the lower limbs, at least 5 cm long and documented by ultrasonographic investigation or other objective methods. Treatment should be initiated as soon as possible following diagnosis and after exclusion of concomitant DVT or superficial-vein thrombosis within 3 cm from the saphenofemoral junction. Treatment should be continued for a minimum of 30 days and up to a maximum of 45 days in patients at high risk of thromboembolic complications. Patients could be recommended to self-inject the product when they are judged willing and able to do so. Physicians should provide clear instructions for self-injection.

Special populations

Renal impairment

Treatment of superficial-vein thrombosis - Fondaparinux should not be used in patients with creatinine clearance <20 ml/min. The dose should be reduced to 1.5 mg once daily in patients with creatinine clearance in the range of 20 to 50 ml/min. No dosage reduction is required for patients with mild renal impairment (creatinine clearance >50 ml/min). The safety and efficacy of 1.5 mg has not been studied.

Hepatic impairment

 Treatment of superficial-vein thrombosis - The safety and efficacy of fondaparinux in patients with severe hepatic impairment has not been studied, therefore fondaparinux is not recommended for use in these patients.

Low body weight

 Treatment of superficial-vein thrombosis - The safety and efficacy of fondaparinux in patients with body weight less than 50 kg has not been studied, therefore fondaparinux is not recommended for use in these patients.

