9.5 Protocol Amendment

This 20th November 2012 version of the protocol had two main amendments incorporated:

a. The present status for fondaparinux as a treatment for SVT across Europe, depending on several factors such as reimbursement or local prescription practices, means that it has been only possible to identify four countries to deploy the described study. As a consequence, the scope of the study described in this protocol has been amended to focus on four countries instead of five. In order to maintain the same patient sample (840 patients in total), the protocol now describes the recruitment of an average of fifteen sites per country, with a higher number of physicians overall per country.

b. The study timeline in the present version of the protocol has been updated to reflect the additional time associated with defining and implementing the requested feasibility study, identifying and agreeing the final selection of countries.

The milestones in section 7.4 have been updated to reflect the remaining study timeline.

This latest version of the protocol amendment addresses the uncertainty on the specificity of renal information after completion of feasibility in Germany, Slovenia and Greece. This led to the inclusion of a row 'serum creatinine' in the feasibility CRF and also the extension of the first question in the patient history section to include severity of renal function.

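### The endpoint wording accepts 2.5 mg or 1.5 mg without a renal condition, although the prescribing information that it is meant to measure makes dose depend on creatinine clearance

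*Supplement*

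**What the plan says.** The dose component is worded in several ways.

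- **Section 2, primary endpoint:** "the correct dose of fondaparinux [either 2.5 or 1.5mg] was prescribed". No renal condition is attached.
- **Section 2, dose secondary endpoint:** patients "for whom either 2.5mg or 1.5mg fondaparinux was prescribed". Again there is no renal condition.
- **Section 4.3:** "the correct dose of fondaparinux (2.5mg or 1.5mg) was prescribed", glossed in the same sentence as "adherence to fondaparinux prescribing information – see Appendix 9.1".
- **Section 5.2.1:** "ensuring that the recommended dose of fondaparinux is prescribed". Section 5.2.2 also refers to the recommended dose. Section 1.2 ties 1.5 mg to renal impairment.
- **Appendix 9.1 (prescribing information):** "The dose should be reduced to 1.5 mg once daily in patients with creatinine clearance in the range of 20 to 50 ml/min"; "Fondaparinux should not be used in patients with creatinine clearance <20 ml/min"; above 50 ml/min it says that no reduction is required.

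The CRF in Appendix 9.3 records renal impairment and its severity, serum creatinine, creatinine clearance, age, weight and gender. Section 9.5 reports that renal information was uncertain after feasibility, and that this led to "the extension of the first question in the patient history section to include severity of renal function". No section scores dose by renal function. The only sensitivity analysis of the primary endpoint concerns thrombus length and distance from the junction.

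**The concern.** The study answers an EU approval commitment to evaluate whether physicians follow the prescribing information on diagnosis and dosing. Section 4.3 names Appendix 9.1 as the standard, but the dose rule written in Section 2 is looser than that standard. Two analysts could score the same chart differently, one accepting either dose and one checking it against clearance. If the Section 2 wording is followed, prescriptions that conflict with the appendix because of renal function are counted as adherence to it, in the primary endpoint and in the dose secondary endpoint. The renal fields are collected, but no stated analysis uses them.

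**Working it through.** **1. Which combinations are affected.** Set the either-dose wording against Appendix 9.1, for a patient who had imaging before treatment:

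| Creatinine clearance | Prescribed | Section 2 wording | Against Appendix 9.1 |
|---|---|---|---|
| <20 ml/min | 2.5 or 1.5 mg | adherent | conflict |
| 20–50 ml/min | 2.5 mg | adherent | conflict |
| 20–50 ml/min | 1.5 mg | adherent | agrees |
| >50 ml/min | 2.5 mg | adherent | agrees |
| >50 ml/min | 1.5 mg | adherent | weaker case: no reduction is required |

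Patients without prior imaging, and patients given 5, 7.5 or 10 mg, fail under both scorings and do not contribute.

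**2. Direction.** Every patient who passes the appendix-concordant rule was given 2.5 or 1.5 mg and so also passes the either-dose rule. Hence either-dose adherence = concordant adherence + d, with d ≥ 0.

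**3. Size.** d = P(imaged) × P(affected renal band, given imaged) × P(conflicting 2.5 or 1.5 mg, given imaged and in that band). None of the three is in the documents. Assumed ranges: 80–100%, 2–20% and 25–100%.

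- Low: 0.80 × 0.02 × 0.25 = 0.004, or 3.4 of 840 patients.
- Intermediate: 1.00 × 0.10 × 0.50 = 0.05, or 42 of 840.
- High: 1.00 × 0.20 × 1.00 = 0.20, or 168 of 840.

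**4. The plan's own figures.** Table 3 gives the power per country for a lower 95% limit above 60% when adherence is 80%. I simulated 20,000 data sets per cell: exchangeable correlated binary data, an intercept-only GEE with robust standard error, and a confidence interval on the logit scale. Of the 16 cells, 13 reproduce within 0.02. For 30 physicians × 7 patients at intra-class correlation (ICC) 0.2 the result is 0.987 against the stated 0.974; for 19 × 7 at ICC 0.3 it is 0.823 against 0.804. Three Scenario 3 cells come out 0.022 to 0.028 above the stated value. The power figures are not in question here.

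**5. What d would do against the 60% bound.** These are illustrations, with d chosen. The d = 0 values come from a separate run of the same simulation.

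- If either-dose adherence is 0.80 and concordant adherence is 0.80 − d, power for the concordant version is:

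| d | 30 × 7, ICC 0.2 | 19 × 7, ICC 0.3 |
|---|---|---|
| 0 | 0.986 | 0.824 |
| 0.02 | 0.959 | 0.731 |
| 0.05 | 0.862 | 0.574 |
| 0.10 | 0.530 | 0.307 |

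- If concordant adherence is exactly 0.60 and the either-dose rule is used (30 × 7, ICC 0.2), the chance that the lower limit exceeds 60% is 0.031 at d = 0, 0.068 at d = 0.02 and 0.181 at d = 0.05.

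**The case against.** The strongest reply is that renal-specific scoring was intended. Section 4.3 says correct dose and points to Appendix 9.1, Section 5.2.1 says recommended dose, Section 1.2 ties 1.5 mg to renal impairment, and the latest amendment extended renal data collection. The detailed rule could also belong in a separate analysis plan, which is not shown. This stands in part. A reader might infer that the protocol has settled on ignoring renal function, and the documents do not support that: the wording is inconsistent rather than uniformly loose. But Section 2 writes the either-dose rule out in both endpoints, and an analysis plan could not follow it and Appendix 9.1 together.

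A second reply is that the rationale's stated safety worry is use of the higher DVT doses, which the either-dose rule does detect. That is fair, but the outcome is still labelled as adherence to the whole dosing text.

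A reader might also infer that every renal dosing error raises reported adherence. It does not: a patient without imaging, or given 5 to 10 mg, already counts as non-adherent.

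Finally, renal data may be incomplete. The CRF allows not-assessed and do-not-know answers, and nothing maps moderate or severe impairment to the clearance bands. That limits how a concordant analysis can be done, but does not remove the need for one.

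**Conclusion.** The point holds as an inconsistency in the definition of the primary endpoint and of the dose secondary endpoint. Under the Section 2 wording, the estimate can only equal or exceed adherence to Appendix 9.1 on dose, by exactly d for the primary endpoint. The firm conflicts are 2.5 mg at 20–50 ml/min and either dose below 20 ml/min; 1.5 mg above 50 ml/min is a softer one. The range of about 0.4 to 20 percentage points rests wholly on assumed inputs, so it shows only that the excess could be trivial or decisive. No particular inflation can be claimed from the documents, and Table 3 is not shown to be wrong. Which dose is clinically right is outside this point.

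**What to change.** Reconcile the dose wording in Sections 1.2, 2, 4.3, 5.2.1 and 5.2.2 with Appendix 9.1, and state one scoring rule for the primary endpoint.

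- Prespecify and report both scorings, either-dose and Appendix 9.1-concordant, overall and per country.
- Base the concordant scoring on the creatinine clearance recorded on the CRF or, failing that, on clearance derived by a named formula from CRF creatinine, age, weight and gender.
- State how 1.5 mg above 50 ml/min is classified.
- Where renal function was not assessed, give bounds: all such patients concordant, then all discordant.
- Do not use the mild/moderate/severe category as a substitute unless its mapping to the clearance bands is defined.

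The cost is a change of wording and a little more analysis, with no new CRF fields. The adherence figure may be lower, and the bounds will be wide if many charts lack renal results.

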1.2. Rationale

Fondaparinux is an anticoagulant used in the prevention and treatment of thromboembolic disease. It has recently been approved in the European Union (EU) for the treatment of patients with isolated SVT, i.e. without concomitant DVT, of the lower limbs. As part of EU approval, GlaxoSmithKline (GSK) committed to evaluate physicians' adherence to fondaparinux prescribing information regarding proper diagnosis and dosing for the treatment of SVT. This includes demonstration that physicians are prescribing fondaparinux at the recommended dose (2.5mg, or 1.5mg in patients with renal impairment), especially given the extended duration of treatment and the higher risk of bleeding which may result if the higher DVT treatment doses are used in this patient population. In addition, the study will assess whether physicians have performed a compression ultrasound (CUS), or other diagnostic imaging procedures, in order to rule out concomitant DVT, which should be treated with a higher dose (5mg, 7.5mg, 10mg).

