4.4. Data Collection

Prior to the start of data collection, the lead investigator of each participating site will have received the Study Protocol and a copy of the CRF for reference. Once the study protocol has been approved by the relevant regulatory body and ethics committee (if applicable) in each country and contracts are

finalised, an initiation telephone call will be organised with the lead investigator in each participating site.

All CRFs received will be tracked and logged on a central database before being processed by Adelphi Real World (ARW) Data Management teams. Sites will regularly be followed-up in order to facilitate the data collection process.

The following data (but not limited to) will be collected by the site abstractors onto CRFs:

- Patient demographics
- Relevant medical history
- Diagnostic procedures performed
- SVT characteristics
- Initial fondaparinux dose, administration frequency and duration of treatment (planned/actual if known). If a dose other than 2.5mg is prescribed/administered, the rationale for this will be requested
- Absence/presence of DVT and relevant details
- Renal Function.

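### The dose rule in the primary endpoint accepts 2.5 mg or 1.5 mg for any patient, so read as written it counts doses that do not match renal function as adherence to Appendix 9.1

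*Supplement*

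**What the plan says.** Section 2 states the dose part of the primary endpoint as "the correct dose of fondaparinux [either 2.5 or 1.5mg] was prescribed". The secondary dose endpoint in the same section counts patients "for whom either 2.5mg or 1.5mg fondaparinux was prescribed". Section 4.3 repeats the pair of doses and equates the result with following the label: "the correct dose of fondaparinux (2.5mg or 1.5mg) was prescribed (i.e. adherence to fondaparinux prescribing information – see Appendix 9.1".

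The label text in Appendix 9.1 makes the choice between the two doses depend on renal function:
- Middle band: "The dose should be reduced to 1.5 mg once daily in patients with creatinine clearance in the range of 20 to 50 ml/min"
- Upper band: patients whose clearance exceeds 50 stay on the usual 2.5 mg.
- Lower band: "Fondaparinux should not be used in patients with creatinine clearance <20 ml/min"

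Other places point towards matching. Section 1.2 speaks of "prescribing fondaparinux at the recommended dose (2.5mg, or 1.5mg in patients with renal impairment". Section 4.3 describes the secondary dose outcome as the correct dose, and Sections 5.2.1 and 5.2.2 speak of the recommended dose. The CRF in Section 9.3 asks about renal impairment and its severity, serum creatinine and creatinine clearance. Section 9.5 records that the severity item was added because of uncertainty about renal information. No section says how these fields enter the scoring of a dose.

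**The concern.** The study answers an EU commitment on diagnosis and dosing, and renal function is the label's only rule for choosing between the two accepted doses. If the endpoint accepts either dose for everyone, it cannot detect a wrong choice between them, yet the result would be reported as adherence to the label.

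Two analysts could follow this protocol and report different primary results, one with matching and one without. No planned analysis would show the gap, because the only sensitivity analysis of the primary endpoint (Sections 2, 4.3 and 5.2.1) adds thrombus length and junction distance. The data query does not catch it either. Section 4.4 says "If a dose other than 2.5mg is prescribed/administered, the rationale for this will be requested", so 2.5 mg given to a patient who should have had 1.5 mg prompts no question.

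**Working it through.** **1. The plan's own figures.** Table 3 gives per-country power, at adherence 0.80 and intra-class correlation (ICC) 0.2, of 0.974 (30 physicians with 7 patients each) and 0.891 (19 with 7). A simulation of 20,000 data sets per scenario, with an intercept-only GEE, robust standard errors and a logit-scale interval, gave 0.985 and 0.904. The power figures are not in dispute. The question is what is being counted.

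**2. The rule against the label.**

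| Creatinine clearance (ml/min) | Appendix 9.1 | Accepted as written | Accepted but discordant |
|---|---|---|---|
| above 50 | 2.5 mg | 2.5 or 1.5 mg | 1.5 mg |
| 20 to 50 | 1.5 mg | 2.5 or 1.5 mg | 2.5 mg |
| below 20 | no use | 2.5 or 1.5 mg | both |

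**3. Direction.** Every chart that passes the matched rule also passes the either-dose rule. With the same denominator, the matched proportion cannot exceed the either-dose proportion.

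**4. Size per unit of mismatch.** Let d be the share of imaging-and-dose-adherent charts whose dose does not match renal function. Taking the plan's 80% as the either-dose proportion:

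matched proportion = 0.80 × (1 − d)

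For d = 1% this is 0.792, a drop of 0.8 points. In charts, that is 0.80 × 210 × 0.01 = 1.7 of 168 in a country at target, or 0.80 × 840 × 0.01 = 6.7 of 672 overall.

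**5. Illustration of d.** The documents do not give d. Assume that a share q of patients has clearance of 50 or less, that a share w of those received a non-matching 2.5 or 1.5 mg dose, independently of imaging, and that nobody above 50 received 1.5 mg. Then d = q × w. With w from 25% to 100%:
- q = 5%: matched adherence 0.79 to 0.76
- q = 10%: 0.78 to 0.72
- q = 20%: 0.76 to 0.64

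**6. Compared with the precision.** With 7 patients per physician and ICC 0.2, the design effect is 1 + 6 × 0.2 = 2.2. The 95% half-width at 80% is:
- per country: 1.96 × √(0.16 × 2.2 / 210) = 8.0 points
- overall: 1.96 × √(0.16 × 2.2 / 840) = 4.0 points

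A shift of one half-width needs d = 8.0 / 0.8 = 10% per country, or 4.0 / 0.8 = 5% overall.

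**7. Effect on the power criterion.** With true matched adherence of 0.76 (d = 5%), the chance that the lower limit exceeds 60% is about 0.91 with 30 physicians and 0.74 with 19. At 0.72 (d = 10%) it is about 0.68 and 0.50. These figures describe planning power only; the protocol sets no pass mark.

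**8. Missing renal data.** If a share u of adherent charts has no usable renal value and all are counted as non-adherent, the figure drops by 80 × u points: 8 points at an assumed u of 10%, 40 points at 50%. The documents do not give u.

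**The case against.** The strongest reply is that matching is what the protocol means. Section 1.2 ties 1.5 mg to renal impairment, the analysis sections use the recommended dose, Section 4.3 points to Appendix 9.1, and renal fields are collected and were extended by amendment. On that reading, the bracketed pair merely lists the two permissible doses, and the label decides which is correct. This is plausible, and it is why the point concerns a rule that needs settling. A reader might infer that the sponsor deliberately chose a lenient endpoint, but the documents do not support that. Still, Section 2 says either dose, and its secondary endpoint does so without the word correct.

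A second reply is that scoring details belong in an analysis plan, and none is shown. That stands for matters such as which creatinine value to use. It does not dispose of the endpoint definition, which the protocol itself states and which conflicts with the label it cites.

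A third reply is that the stated bleeding concern is use of the higher DVT doses, and the either-dose rule does catch those. This is true and limits the importance of the point. It does not make the result adherence to Appendix 9.1.

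A reader might also infer that adherence will be materially overstated, or that the study would miss a 60% target. Neither follows. The mismatch share is unknown, and 60% appears only as the criterion in the power simulations (Section 5.1 and Appendix 9.4). The primary aim is estimation.

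**Conclusion.** The concern holds as an inconsistency between the endpoint as written and the label it claims to measure. Its effect runs in one direction: under the literal rule, adherence to Appendix 9.1 can only be overstated. If matching is intended and applied, there is no bias, but the text still needs correcting.

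The size is 0.8 points per 1% of adherent charts with a mismatched dose, given 80% either-dose adherence and a common denominator. The total cannot be fixed from the documents and would be small if few patients have a clearance of 50 ml/min or less. Because the study is there to estimate adherence, a one-sided error matters even when it is far from 60%. This is something the sponsor should change; it does not invalidate the design.

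**What to change.** **If matching is intended:** in Sections 2 and 4.3, replace the either-dose wording with the Appendix 9.1 rule (2.5 mg above 50 ml/min, 1.5 mg at 20 to 50, no dose correct below 20). Report the either-dose proportion beside the matched one.

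**If it is not:** keep the either-dose endpoint, state that it does not assess renal matching, and add a renally matched sensitivity analysis to Sections 4.3 and 5.2.1.

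The handling of renal data can be:
- Use the recorded creatinine clearance. Where it is absent but serum creatinine is recorded, estimate it by Cockcroft-Gault from age, weight and gender, all on the CRF, and mark it as estimated.
- Flag values dated after the first prescription. The CRF takes only one dated value of each, so no earlier one may be available.
- Make charts with known renal function the main matched result, with the either-dose proportion on the same charts so that the two are comparable. Report the number with no usable value.
- Show charts that were not assessed as non-adherent only as a worst-case bound. The label text as reproduced does not itself require a renal test, and this bound can move the figure a long way.

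The cost is a wording change and one analysis, with no new patients or CRF fields. The sponsor accepts incomplete renal data and a second figure that may be less favourable.

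### Thrombus length and junction distance are defined inconsistently across sections 2, 4.3 and 5.2.1, and the >5 cm rule departs from the protocol's own adherence standard at exactly 5.0 cm

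*Supplement*

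**What the plan says.** Section 2 plans a sensitivity analysis of the primary endpoint "incorporating the length of the thrombus (>5 cm) and/or its distance from the sapheno-femoral junction (>3 cm"), subject to what the feasibility phase shows to be available. It then lists two conditional secondary endpoints: the proportion of patients "for whom the length of thrombus was measured (<5 cm being non-adherence"), and the proportion "for whom the distance from the sapheno-femoral junction was recorded (<3 cm being non-adherence").

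Section 4.3 repeats the sensitivity analysis, "incorporating the length of the thrombus (>5 cm) and/or its distance from the sapheno-femoral junction (>3 cm), pending the availability of the data". For the secondary outcomes it says, for charts where the data exist: "the proportion of patients having a thrombus >5 cm and a distance from the sapheno-femoral junction of at least 3 cm will be estimated".

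Section 5.2.1 describes the sensitivity analysis without cut-offs and joins the two items with *and* where sections 2 and 4.3 have *and/or*. Section 5.2.2 counts length and distance as two of four secondary endpoints and gives no cut-off.

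Section 4.3 refers to Appendix 9.1 (Fondaparinux prescribing information) as the definition of adherence. That text describes an eligible thrombosis as "at least 5 cm long and documented by ultrasonographic investigation or other objective methods", and treatment as starting "after exclusion of concomitant DVT or superficial-vein thrombosis within 3 cm from the saphenofemoral junction".

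**The concern.** Two problems overlap. First, the numerator changes between sections. Section 2 asks whether the chart contains a measurement; section 4.3 asks what the measurement was. Section 2 is also unclear in itself: a thrombus measured at 4 cm was measured, yet the parenthesis calls it non-adherent.

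Second, the cut-offs are strict in some places and inclusive in others. A patient whose length is exactly 5.0 cm satisfies the prescribing information that the study uses as its yardstick, but would be coded as non-adherent in the sensitivity analysis and would not count in the section 4.3 secondary outcome.

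At stake are the only stated sensitivity analysis of the primary endpoint and two of the four secondary endpoints, in a study carried out to meet an EU approval commitment. An analyst working from section 2 and another working from section 4.3 could report different figures from the same case report forms, and both would be following the protocol.

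**Working it through.** The protocol gives no expected value, precision or power for the length and distance endpoints, so there is no stated figure to reproduce. The main check sets the texts side by side.

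| Place | What is assessed | Length exactly 5.0 cm | Distance exactly 3.0 cm |
|---|---|---|---|
| Appendix 9.1, prescribing information | value | meets it | not explicit |
| Section 2, sensitivity analysis | value (>5, >3) | fails | fails |
| Section 2, secondary endpoints | measured / recorded, with <5 and <3 non-adherent | not non-adherent | not non-adherent |
| Section 4.3, sensitivity analysis | value (>5, >3) | fails | fails |
| Section 4.3, secondary outcomes | value (>5, at least 3) | fails | passes |
| Sections 5.2.1 and 5.2.2 | no cut-off | undefined | undefined |

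For length, two rules compete: >5 cm and at least 5 cm. For distance, >3 cm and at least 3 cm compete, and the appendix phrase "superficial-vein thrombosis within 3 cm from the saphenofemoral junction" does not say how exactly 3.0 cm is classed. Section 4.3 also joins length and distance in one phrase, which could be read as a joint proportion, whereas sections 2 and 5.2.2 treat them as separate endpoints.

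To see how much the definitions could matter, let r be the share of charts with length recorded, g the share of recorded lengths above 5 cm, and h the share of recorded lengths exactly 5.0 cm. None of these is in the documents. The assumed ranges are r = 0.5–1.0, g = 0.6–0.9 and h = 0.02–0.10.

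- Measured = r
- >5 cm among all patients = r × g
- At least 5 cm among all patients = r × (g + h)
- Among recorded charts only: g, or g + h

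*Measured versus >5 cm among all patients.* The gap is r − r × g = r × (1 − g). Smallest: 0.5 × (1 − 0.9) = 0.05. Largest: 1.0 × (1 − 0.6) = 0.40. That is 5 to 40 points.

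*Strict versus inclusive length cut-off, all patients.* The gap is r × h. Smallest: 0.5 × 0.02 = 0.01. Largest: 1.0 × 0.10 = 0.10. That is 1 to 10 points, or about 8 to 84 of the 840 planned patients. It is 0 if no charted length is exactly 5.0 cm.

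*One worked case,* r = 0.7, g = 0.8, h = 0.05:

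- Measured: 70%
- >5 cm among all: 0.7 × 0.8 = 56%
- At least 5 cm among all: 0.7 × 0.85 = 59.5%
- >5 cm among recorded: 80%
- At least 5 cm among recorded: 85%
- Patients changing code at the boundary: 0.7 × 0.05 × 840 ≈ 29

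*A milder case,* r = 1.0, g = 0.9, h = 0.02: measured 100%, >5 cm 90%, at least 5 cm 92%.

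*For scale,* the half-width of an overall 95% confidence interval at p = 0.8, with 840 patients, 7 per physician and intra-class correlation ρ, is approximately 1.96 × √(0.8 × 0.2 × (1 + 6ρ) / 840). With ρ = 0.1 this is 3.4 points; with ρ = 0.3 it is 4.5 points. On the assumed ranges, the choice between documentation and value, or between denominators, would usually exceed that. The boundary choice alone often would not.

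**The case against.** The strongest reply is that this is a narrow wording conflict in conditional, non-primary analyses. Section 2's parenthesis can be read as *measured and not below 5 cm*. On that reading its numerator differs from section 4.3 only at exactly 5.0 cm. The case report form collects length and distance in centimetres with a *Not recorded* box, so any definition can be computed later and no data are lost. An analysis plan, which is not shown, would ordinarily settle denominators and missing-value coding, so their absence here is not a fault in itself. All of this stands and limits the weight of the point. It does not remove the disagreement between sections, or the mismatch between >5 cm and the named standard.

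A typographical loss of an *at least* sign in reading the PDF is unlikely. That sign survives in section 5.1 and Appendix 9.4, and section 4.3 sets >5 cm beside the words for at least 3 cm in one sentence.

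A reader might infer four stronger things that the documents do not support:

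- *That three length rules compete.* Calling <5 cm non-adherent is the complement of at least 5 cm, so there are two. The same holds for <3 cm and at least 3 cm.
- *That and/or lets the items be picked once results are known.* Section 2 ties the choice to the feasibility phase, which precedes the main study, and its questionnaire ticks only whether length and distance are in the chart, not their values. What can be said is that no rule for sufficient availability is stated and that section 5.2.1 uses a different conjunction.
- *That sections 2 and 4.3 code Not recorded in opposite ways.* Neither states how it is coded, and the condition in section 4.3 may simply restrict that estimate to charts with a value.
- *That the results would certainly differ greatly, because charted lengths pile up on whole centimetres.* The documents give no recording rate, no length distribution and nothing on rounding.

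**Conclusion.** The point holds as an internal inconsistency. Sections 2 and 4.3 give different numerators for the same two secondary endpoints. The strict length cut-off in the sensitivity analysis and in the section 4.3 secondary outcome conflicts with Appendix 9.1 and with section 2's secondary endpoint for a length of exactly 5.0 cm. The distance cut-off differs within section 4.3 itself, and the joining word differs between sections 2 and 4.3 on one side and 5.2.1 on the other.

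Its size is unknown. The ranges in the working (about 1–10 points for the length boundary, about 5–40 points for measured against >5 cm among all patients) rest wholly on the assumed r, g and h, and the larger one also requires reading section 2 as a pure documentation rate. The primary endpoint, its definition and the sample size are not affected. It is worth correcting before analysis, but does not threaten the main result.

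**What to change.** Reconcile sections 2, 4.3 and 5.2 as follows.

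- Give each item one analysis cut-off, consistent with Appendix 9.1 as the adherence standard the protocol itself names, and use it in both the sensitivity analysis and the secondary endpoint. State how a value exactly on the boundary is coded. For distance the appendix wording leaves this open, so the sponsor must settle it explicitly.
- Report the percentage with the item recorded separately from the percentage meeting the criterion. State the denominator of the latter and how *Not recorded* is handled.
- Once feasibility has shown what is available, name which items enter the sensitivity analysis and whether they are required singly or together, with the same wording in all three sections.

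The cost is wording changes and a few extra table rows. The case report form already collects what is needed, so no new data collection follows.
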